Subjects are informed during the consenting process, and in the consent form, that their participation is voluntary and they may withdraw consent at any time and for any reason. If subjects wish to withdraw from the study, they will be asked, but not required, to perform the off-study procedures/blood draws. They will be again informed that their decision to participate or not participate at any time will not affect their routine medical care or any other benefits to which they were otherwise entitled. In addition, subjects will be removed from study participation if there is a concern for patient safety, as described above, if they are unable to comply with study procedures, or if the study is terminated by local or national regulatory agencies.

F. Roles and Responsibilities of Study Personnel at UWCCC

Study Principal Investigator:

[name] MD PhD, Associate Professor of Medicine, is a genitourinary medical oncologist, with a clinical research and laboratory interest in immune-based therapies for prostate cancer. He has served as the principal investigator for several other clinical trials, and has had formalized training in the ethics and conduct of clinical trials and human subjects protection. He will be overall responsible for the conduct of the trial and its analysis, but will not participate in patient accrual, treatment of patients on study, or interpretation of clinical data. [name] involvement will center on the scientific aspects of the project, including overall trial design and analysis of samples from the trial. [name] will participate as author on any manuscripts derived from this research.

UWCCC Local Principal Investigator:

[name] MD, Associate Professor of Medicine, is a genitourinary medical oncologist with a primary interest in genitourinary cancer clinical trials research. He will be the UWCCC local principal investigator for this study. As UWCCC local PI he will be responsible for activities involving direct patient care and interaction, including recruitment, consent, clinical care and adverse event reporting. The UWCCC local PI will also assume the role of principal investigator on the protocol and UW HS-IRB submission, working with the UW HS-IRB as the responsible investigator to obtain and maintain UW HS-IRB approval for the study. The UWCCC local PI will also be responsible for reviewing significant adverse events that occur at UWCCC and will oversee the care provided by the UWCCC co-investigators on this study.

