For each of the DNA immunizations: 0.6 mL of 0.2 mg/mL pTVG-HP will be withdrawn and used to reconstitute 250 µg GM-CSF. 0.25 mL will then be drawn into each of two tuberculin syringes. This effectively provides a 100-µg dose of DNA and 208 µg GM-CSF.

5. Patient Selection

A. Inclusion Criteria

1. Age \geq 18 years.
2. Histologically confirmed diagnosis of prostate cancer (adenocarcinoma of the prostate)
3. Metastatic disease as evidenced by the presence of soft tissue and/or bone metastases on imaging studies (CT of abdomen/pelvis, bone scintigraphy)
4. Castrate-resistant disease, defined as follows:
 - a. All patients must have received standard of care androgen deprivation treatment before trial entry (surgical castration versus GnRH analogue or antagonist treatment), and subjects receiving GnRH analogue or antagonist must continue this treatment throughout the time on this study.
 - b. Patients may have been treated previously with a nonsteroidal antiandrogen, with evidence of disease progression (defined below) subsequently. Subjects must be off use of anti-androgen for at least 4 weeks (for flutamide) or 6 weeks (for bicalutamide or nilutamide) prior to registration.

Subjects who demonstrate an anti-androgen withdrawal response, defined as a \geq 25% decline in PSA within 4-6 week of stopping a nonsteroidal antiandrogen are not eligible until the PSA rises above the nadir observed after antiandrogen withdrawal.
 - c. Castration levels of testosterone ($<$ 50 ng/dL) within 2 weeks of registration
5. Progressive disease while receiving androgen deprivation therapy defined by any one of the following as per the Prostate Cancer Clinical Trials Working Group 2 (PCWG2) bone scan criteria [49] or RECIST 1.1 during or after completing last therapy:
 - a. PSA: At least two consecutive rises in serum PSA, obtained at a minimum of 1-week intervals, and each value \geq 2.0 ng/mL.
 - b. Measurable disease: \geq 50% increase in the sum of the cross products of all measurable lesions or the development of new measurable lesions. The short axis of a target lymph node must be at least 15mm by spiral CT to be considered a target lesion.

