 - c. Non-measurable (bone) disease: The appearance of two or more new areas of uptake on bone scan consistent with metastatic disease compared to previous imaging during castration therapy. The increased uptake of pre-existing lesions on bone scan will not be taken to constitute progression, and ambiguous results must be confirmed by other imaging modalities (e.g. X-ray, CT or MRI).

6. Must have ≥ 3 serum PSA values obtained over at least a 12 week period of time prior to registration, including the day of screening, to calculate a PSA doubling time (<http://www.mskcc.org/applications/nomograms/prostate/PsaDoublingTime.aspx>). Note: PSA's are not required to be obtained at the same laboratory. Use all PSA values that have been done in last 6 months to calculate PSA doubling time.
7. Life expectancy of at least 6 months
8. Patients must have an ECOG performance status of 0, 1, or 2.
9. Adequate hematologic, renal and liver function as evidenced by the following within 14 days of first peripheral blood collection for Sipuleucel-T.

WBC	$\geq 2000 / \text{mm}^3$
ANC	$\geq 1000 / \text{mm}^3$
HgB	$\geq 9.0 \text{ gm/dL}$
Platelets	$\geq 100,000 / \text{mm}^3$
Creatinine	$\leq 2.0 \text{ mg/dL}$
AST, ALT	$\leq 2.5 \times$ institutional upper limit of normal
10. Negative serology tests for HIV Ab/Ag Combo and for active Hepatitis B and Hepatitis C, within 14 days of first peripheral blood collection for Sipuleucel-T.
11. Patients must be at least 4 weeks from any prior treatments and have recovered (to $<$ Grade 2) from acute toxicity attributed to this prior treatment
12. Patients must be informed of the experimental nature of the study and its potential risks, and must sign an IRB-approved written informed consent form indicating such an understanding

B. Exclusion Criteria

1. Small cell or other variant prostate cancer histology
2. Patients may not be receiving other investigational agents or be receiving concurrent anticancer therapy other than androgen deprivation
3. Symptomatic metastatic disease, as defined by the need for opioid analgesics for the treatment of pain attributed to a prostate cancer metastatic lesion; patients receiving opioids must receive approval from the PI for eligibility
4. Patients may not have been treated with prior sipuleucel-T
5. Treatment with any of the following medications within 28 days of registration, or while on study, is prohibited:

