The primary endpoint of the trial will be an immunological endpoint – the detection of augmented numbers of PAP-specific effector (IFN γ -secreting and/or granzyme B-secreting) and memory (proliferating) T-cell immune response after immunization, using blood obtained at 6 months for the primary analysis compared with pre-treatment. Immune response will be determined as a static time point at 6 months, and “durable” immune responses will also be determined by evaluation at 3, 9, and 12 months after study entry.

All subjects will undergo radiographic imaging (CT of abdomen and pelvis and bone scan) prior to treatment, and at 3-month intervals (or as clinically indicated). Radiographic disease progression will be defined using both RECIST 1.1 and PCWG2 published criteria [49], as detailed in Section 7. Based on the prior trials leading to the approval of sipuleucel-T, and because immune therapies are expected to require up to several months before radiographic responses or stabilization might be observed, the radiographic studies obtained at 3 months will not be used to define progression, rather will be used as the baseline for future comparison. That is, while baseline studies will be obtained prior to study registration, and radiographic progression may be expected in 50% of patients at 3 months, this will not be used to define progression necessitating patients come off study, rather disease progression occurring after this initial 3-month period. Time to progression will be determined from registration for all subjects. 1-year progression-free survival will be calculated for each treatment arm, as well as the median progression-free survival.

PSA doubling times will be calculated from all available values obtained within 3-6 months from the same clinical laboratory (when feasible) prior to study enrollment, up to and including the baseline value, and used to determine a pre-treatment PSA doubling time. Similarly, a post-treatment doubling time will be calculated from all PSA values obtained beginning with the PSA value at day 1 and continuing until the end-of study (or 1-year) value.

7. Measurement of Effect

A. Malignant Disease Evaluation

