200,000 cells/well of a 96-well plate, and all spots will be counted (i.e. screening for events among $\sim 20 \times 10^6$ total PBMC). Multiple replicates to determine standard deviation are not feasible. Other methods of CTC enumeration, such as by flow cytometry, may also be used.

C. Serum PSA Doubling Time Response

See Section 12 for further details. Serum PSA doubling-time response will be considered a secondary endpoint. The pre-treatment serum PSA doubling time will be calculated from all serum PSA values available for the three-month period prior to study treatment, not on other treatments for prostate cancer, up to and including the PSA value obtained at screening, using the Memorial Sloan-Kettering Cancer Center nomogram (<http://www.mskcc.org/applications/nomograms/prostate/PsaDoublingTime.aspx>). The post-treatment serum PSA doubling time will be calculated using the same algorithm and using all serum PSA values available during the time patients are on study beginning with the PSA value obtained at day 1.

REPORTING AND RESPONSE DEFINITION: PSA doubling times for the pre-treatment and post-treatment periods will be defined as above. An increase in the PSA doubling time to at least double the baseline value will be defined as a PSA doubling time “response” [64].

11. Reporting Adverse Events

Please see section 14 below, which contains in detail the policy and procedures for patient safety monitoring and adverse event reporting.

A. Definition

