C.2.4. PSA Response

PSA complete response will be defined a decrease in PSA to <0.2 ng/mL. The decrease must be confirmed with PSA measurement a minimum of four weeks later (confirmed PSA CR). PSA partial response will be defined as reduction of at least 50% in baseline PSA.

C.2.5. PSA Doubling Time

PSA doubling time (PSADT) will be defined as the time it takes for the PSA value to double. PSADT will be calculated for each patient pre-treatment and post-treatment. The pre-treatment PSADT will be calculated from all available values obtained within 3-6 months prior to study enrollment, up to and including the baseline value. The post-treatment PSADT will be calculated from all PSA values obtained beginning with the PSA value at day 1 and continuing until the end-of study value. The pre-treatment and post-treatment PSADT will be calculated for each patient as the log 2 divided by the slope of the log PSA line, based on the linear regression model of log (PSA value) on time.

C.2.6. Evaluable for Immune Response

All patients who complete sipuleucel-T treatment at weeks 0, 2, and 4, and who have an immune response assessment at month 6 will be evaluable for immune response.

C.2.7. Analysis Populations

The ITT population consists of all patients who are randomized. The per-protocol population is defined as all patients who have been treated according to protocol, i.e., all inclusion/exclusion criteria are satisfied, and adequate treatment compliance of sipuleucel-T treatment and vaccine (pTVG-HP) is achieved.

D. Study Design

The study is designed as a randomized, two-arm, open-label, single institution pilot trial. Study arms will be defined as follows:

Arm 1: sipuleucel-T – administered intravenously (i.v.) per standard of care biweekly, weeks 0, 2, and 4.

Arm 2: sipuleucel-T – administered intravenously (i.v.) per standard of care biweekly, weeks 0, 2, and 4
 pTVG-HP (100 µg) with rhGM-CSF (208 µg) administered intradermally (i.d.) biweekly 4 times, then every 3 months to complete a 1-year treatment period (i.e. weeks 6, 8, 10, 12, then months 6, 9)

Eligible subjects will be randomly assigned in 1:1 fashion to either Arm 1 or Arm 2.

E. Randomization and Stratification

Eligible patients will be randomized to the two study arms with an allocation ratio of 1:1. The randomization will be based on permuted blocks of size 2-4, stratified by estimated survival (< 18 months, ≥ 18 months) using the Halabi nomogram [50].

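### Two definitions of the pre-treatment PSA doubling time: 12.C.2.5 and 6.B take all values, 10.C only off-treatment values, so the analysed baseline may mix on-drug and off-drug PSA in recently washed-out men

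*Combined protocol and SAP*

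**What the plan says.** Four places specify which PSA values make up the pre-treatment PSADT.

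- 5.A item 6 (entry check): "Must have ≥ 3 serum PSA values obtained over at least a 12 week period of time prior to registration, including the day of screening", and then "Use all PSA values that have been done in last 6 months to calculate PSA doubling time".
- 6.B: "PSA doubling times will be calculated from all available values obtained within 3-6 months" before enrolment, from one laboratory when feasible.
- 12.C.2.5 (analysis definition): "The pre-treatment PSADT will be calculated from all available values obtained within 3-6 months prior to study enrollment".
- 10.C: values available "for the three-month period prior to study treatment, not on other treatments for prostate cancer". This section also points the reader to Section 12 for more detail.

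Only 10.C has an off-treatment condition. 12.G.4.4 gives the estimator (log 2 divided by the least-squares slope of log PSA) and does not add the condition. It replaces negative PSADT estimates with a fixed positive value, for example the largest one observed.

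Two entry rules bear on this. Item 4b: "Subjects must be off use of anti-androgen for at least 4 weeks (for flutamide) or 6 weeks (for bicalutamide or nilutamide) prior to registration". Men whose PSA falls by 25% or more on withdrawal "are not eligible until the PSA rises above the nadir observed after antiandrogen withdrawal". Item 11: "Patients must be at least 4 weeks from any prior treatments". No section says that values from the on-drug or withdrawal phase are dropped.

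**The concern.** An analyst who follows 12.C.2.5 and one who follows 10.C can obtain different baselines from the same patient. Under 12.C.2.5, a man who recently stopped an anti-androgen may contribute on-drug values, a step at withdrawal and off-drug values, all fitted by one straight line. That slope does not estimate untreated growth. The post-treatment slope should be off-drug, because 5.B item 2 bars concurrent anticancer therapy other than androgen deprivation. In such a man the pre/post ratio partly reflects withdrawal of the earlier drug.

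At stake are secondary objective 3, the within-arm paired tests in 12.G.4.4, and the rule in 10.C that counts a doubling of PSADT as a response.

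**Working it through.** The plan states no power or precision figure for PSADT, so there is none to reproduce.

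**1. How much of the record can be on-drug.** Share = (look-back − washout) / look-back, at the minimum washouts in item 4b, for a man on the drug until then.

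| Look-back | 6-week washout | 4-week washout |
|---|---|---|
| 12 weeks (item 6 minimum) | 6/12 = 50% | 8/12 = 67% |
| 13 weeks | 7/13 = 54% | 9/13 = 69% |
| 26 weeks | 20/26 = 77% | 22/26 = 85% |

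At minimum washout he can meet the 12-week span only by using on-drug values.

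**2. Effect on the fitted slope.** Assumptions, not from the documents: PSA at weeks −24, −20, −16, −12, −8, −6, −4, −2 and 0; constant true growth; drug stopped at week −6; all later values multiplied by f. The 25% fall (f = 0.75) borrows item 4b's threshold as a scale. With s = 1 after the stop and 0 before,

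fitted slope = true slope + ln(f) × k, where k = Σ(t − t̄)s / Σ(t − t̄)².

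- 6-month window (nine values): k = 24.67/555.6 = 0.0444.
- 13-week window (six values): k = 10.0/93.3 = 0.1071.

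True slopes: 6.0 months = 0.6931/26 = 0.02666 per week; 3.0 months = 0.6931/13 = 0.05332 per week. ln(0.75) = −0.2877.

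| True PSADT | 6-month window | 13-week window |
|---|---|---|
| 6.0 | 0.02666 − 0.01277 = 0.01389, or 11.5 months | 0.02666 − 0.03082 = −0.00416, negative |
| 3.0 | 0.05332 − 0.01277 = 0.04055, or 3.9 months | 0.05332 − 0.03082 = 0.02250, or 7.1 months |

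This man's PSA rises from week −4 to −2 to 0. Item 4b would admit him, and he would meet the PSA progression rule in item 5a if those values are 2.0 ng/mL or more.

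**3. A gentler scenario.** Monthly values, true PSADT 6.0 months, fall phased in over four weeks.

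| Washout, fall | 6-month window | 3-month window |
|---|---|---|
| 6 weeks, none | 6.0 | 6.0 |
| 6 weeks, 10% | 6.9 | 8.7 |
| 6 weeks, 20% | 8.2 | 17.6 |
| 6 weeks, 30% | 10.4 | negative |
| 12 weeks, 20% | 10.0 | 15.5 |

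Falls below the 25% rule, which delay nobody's entry, still distort the baseline. So does a washout well above the minimum.

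**4. The opposite direction.** Suppose PSA rises by 30% on stopping (assumed; ln 1.3 = 0.2624). In the step 2 setting a true 6.0 months is then estimated as 4.2 or 2.9. With unchanged true growth, the post/pre ratios are 1.44 (6-month) and 2.05 (13-week). For a true 3.0 months they are 1.22 and 1.53. Only one of the four reaches a doubling.

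**5. Precision of the possible remedies.** Assumed noise SD is 0.10 on log PSA, in the step 2 setting with a 25% fall. Errors are per week; the true slope for 6.0 months is 0.0267.

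| Method | Bias | SE | Root mean square error |
|---|---|---|---|
| All values, one line, 6-month | −0.0128 | 0.0042 | 0.0135 |
| All values, one line, 13-week | −0.0308 | 0.0104 | 0.0325 |
| Three off-drug values only | 0 | 0.0354 | 0.0354 |
| One slope plus level shift, 6-month | 0 | 0.0063 | 0.0063 |
| One slope plus level shift, 13-week | 0 | 0.0194 | 0.0194 |

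With three off-drug values over four weeks, the SE is 0.0354/0.0267 = 1.33 times the slope itself.

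**The case against.** 10.C already carries the off-treatment condition, and its pointer to Section 12 can be read as asking for both sections to be applied together. Nothing says that 12.C.2.5 overrides it. This stands to a degree: a reader might infer that the analysed baseline does contain on-drug values, but the documents support only that it may. The mismatch remains, because an analyst working from Section 12 alone would not see the condition.

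A reader might also take 4 to 6 weeks as the usual gap. Item 4b gives it as a minimum, and prior anti-androgen use is permitted, not required. The number of men affected cannot be derived from the documents. Item 6 is an entry rule and does not define the analysed quantity; 6.B and 12.C.2.5 do.

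It is tempting to say that the flaw manufactures PSADT responders. That needs an assumed 30% rise on stopping, a 13-week window and slow true growth. Item 4b recognises only a decline on withdrawal, which works against showing benefit.

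12.G.4.4 allows rank tests, which limit the pull of extreme values, and names no test for the PSADT response. Both points reduce the consequence. The paired pre/post comparison still uses the distorted baseline.

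Finally, simply restricting to off-drug values could be worse than the problem. Step 5 bears this out for recently washed-out men, so the remedy has to be more than that restriction.

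**Conclusion.** The concern holds as an inconsistency in the current text with a material effect on some men. Two baselines are defined for one secondary endpoint. Under the Section 12 definition, a 25% withdrawal fall at week −6 would turn a true 6.0 months into about 11.5 months on a 6-month window, or a negative estimate on a 13-week window. 12.G.4.4 would then replace the negative value with a fixed positive one. The likely direction after a withdrawal fall is to lengthen the baseline and hide benefit.

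The size rests on assumed PSA timing, constant growth and the assumed step. With no withdrawal effect there is no distortion. Bias between the arms might be inferred, but it is not expected, because randomisation precedes treatment and the baseline problem falls on both arms alike. What remains is added noise and possible chance imbalance with 15 men per arm. The primary immune endpoint and the sample size are unaffected. The correction is worth making before analysis and is not a threat to the trial's main conclusion.

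**What to change.** Put one definition of the pre-treatment PSADT in 12.C.2.5 and align 6.B and 10.C to it. It should state a single window, 10.C's off-treatment condition (ongoing androgen deprivation excepted) and a minimum number of values. In the step 5 example the longer window gives the more precise slope.

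For men whose prior therapy stopped inside the window and whose off-drug values are too few or too close together (for example fewer than three, or spanning under 12 weeks):

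- Fit log PSA over the whole window with one slope plus a level shift at the stop date, provided there are at least two off-drug values and at least four in total. With a single off-drug value the shift absorbs it and the slope is purely on-drug; with three values in total the model is saturated.
- Otherwise flag the baseline PSADT as not estimable off treatment, and report a sensitivity analysis with and without these men.

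Keep item 6 as an entry check, and say that its figure is not the analysis value.

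The cost is wording plus use of the therapy stop date, which eligibility already requires. No visit or sample is added. A few men will have a less precise or missing baseline slope, and the level-shift model assumes the same growth rate on and off the drug.

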Evidence that the toxicity rate is excessive will be considered sufficient if the lower limits of the 90% one-sided confidence intervals for the estimates of the true toxicity rates exceed the toxicity limits defined above (i.e., 20% for Grade 3 events and 10% for Grade 4 events), after the first 5 patients have been accrued. Operationally, this will occur if any of the following events occurs within a study arm: Grade ≥ 3 events (or Grade >1 autoimmune events) are present in at least 3 out of 5, 4 out of 9 (or less), 5 out of 13 (or less), or 6 out of 15 (or less) of the subjects accrued (within a study arm). Furthermore, accrual will be temporarily suspended if any of the following events occur: Grade 4 events are present in at least 2 out of 5, 3 out of 11 (or less), or 4 out of 15 (or less) of the subjects accrued (within a study arm).

If one of these thresholds is reached, accrual will be temporarily suspended and the study will be reviewed by the UW DSMC (data and safety monitoring committee) to consider safety and dose modifications with respect to treatment arm. Once the study is suspended, it would only be reopened if modifications could be made, and approved by the DSMC and the UW-IRB, to assure that patient safety is reestablished. If not, the study would be closed.

B. Endpoints

Patients will come off study at the time of radiographic disease progression, with progression being defined only AFTER the first 3-month staging evaluation, at the time of undue toxicity (as defined below), or at the discretion of the patient and treating physician that other therapies for prostate cancer are warranted. Patients should be discouraged from discontinuing protocol treatment for PSA rise only. Patients will continue to have blood drawn for immune studies, as per study calendar, up to one year after screening, even if off study prior to that time. The 6 month visit, in particular, is important to collect for the purpose of endpoint analysis. Subjects who have not come off study earlier for these reasons will come off study at the end of the one-year treatment period.

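### The first toxicity suspension limits lack the 'or less' of the later ones, so an arm with 3 Grade ≥3 or 2 Grade 4 events before its fifth patient reaches no listed limit, although it is certain to cross at patient five

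*Combined protocol and SAP*

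**What the plan says.** Section 6.A (Study Arm Assignment and Toxicity Assessment) gives the rule in two forms.

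- **Criterion.** Toxicity is excessive if the "lower limits of the 90% one-sided confidence intervals for the estimates of the true toxicity rates exceed the toxicity limits defined above" ("20% for Grade 3 events and 10% for Grade 4 events"), and this is applied "after the first 5 patients have been accrued".
- **Operational list, counted within a study arm.** For Grade ≥3 events (or autoimmune events above Grade 1) the limits are "3 out of 5, 4 out of 9 (or less), 5 out of 13 (or less), or 6 out of 15 (or less". For Grade 4 events they are "2 out of 5, 3 out of 11 (or less), or 4 out of 15 (or less".

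The consequence is the same for both lists: "If one of these thresholds is reached, accrual will be temporarily suspended", and the data and safety monitoring committee (DSMC) reviews the study. Events count if at least possibly related to treatment. Short-lived Grade 3 site reactions and fevers or chills are excluded.

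**The concern.** Five of the seven entries act as soon as their count is reached. The two entries for five patients do not. Read with the five-patient clause, the list has no entry for exactly 3 Grade ≥3 events among 3 or 4 patients, or for exactly 2 Grade 4 events among 2 to 4 patients.

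These counts are stronger evidence of toxicity than 3 of 5 or 2 of 5, yet only the weaker evidence triggers suspension. A delayed start usually protects against stopping on sparse data. It cannot do so here, because a cumulative count never falls. At stake is a small number of additional patients entering an arm whose suspension is already settled.

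**Working it through.** **Inputs.** Limit rates 20% and 10%, one-sided 90% confidence and the listed limits (Section 6.A); 15 patients per arm, 30 accrued in 18 months (Section 12.F).

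**1. Reproduce the plan's limits.** The exact (Clopper-Pearson) lower limit for x events in n patients is the 10% quantile of Beta(x, n − x + 1). It exceeds p0 when P(X ≥ x | n, p0) < 0.10.

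| Rule | Listed limit | Lower limit |
|---|---|---|
| Grade ≥3, p0 = 0.20 | 3/5 | 0.247 |
| | 4/9 | 0.210 |
| | 5/13 | 0.2005 |
| | 6/15 | 0.226 |
| Grade 4, p0 = 0.10 | 2/5 | 0.112 |
| | 3/11 | 0.105 |
| | 4/15 | 0.122 |

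All seven satisfy the criterion. One count outside the list also does: 3/6 for Grade ≥3 (tail probability 0.0989), where the list asks for 4 events.

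**2. Same criterion below five patients.**

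| Rule | Count | Lower limit | Against |
|---|---|---|---|
| Grade ≥3 | 3/3 | 0.464 | 0.20 |
| Grade ≥3 | 3/4 | 0.320 | 0.20 |
| Grade 4 | 2/2 | 0.316 | 0.10 |
| Grade 4 | 2/3 | 0.196 | 0.10 |
| Grade 4 | 2/4 | 0.143 | 0.10 |

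Each meets the criterion. If every later patient is event-free, the count at patient five is still 3/5 or 2/5, so crossing is certain once five are accrued.

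**3. How often this arises.** P(X ≥ 3 | n = 4) = 4p³(1 − p) + p⁴. At p = 0.20 this is 0.0256 + 0.0016 = 2.7%; at p = 0.40 it is 17.9%. P(X ≥ 2 | n = 4) is 5.2% at p = 0.10 and 34.8% at p = 0.30.

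**4. Effect of adding 'or less'.** An exact patient-by-patient binomial recursion to 15 patients per arm, each rule taken alone:

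| Rule, true rate | Ever crosses, both versions | Mean accrued, start at 5 | Mean accrued, 'or less' |
|---|---|---|---|
| Grade ≥3, 20% | 14.8% | 14.00 | 13.96 |
| Grade ≥3, 40% | 71.6% | 9.84 | 9.59 |
| Grade 4, 10% | 13.9% | 13.93 | 13.84 |
| Grade 4, 30% | 78.9% | 8.77 | 8.12 |

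The mean savings are about 0.25 (9.84 − 9.59) and 0.65 (8.77 − 8.12) patients. The largest savings are 5 − 3 = 2 patients after 3/3 and 5 − 2 = 3 after 2/2.

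These figures let the five-patient clause hold back every entry. Taken literally, 4/4 Grade ≥3 and 3/3 or 3/4 Grade 4 already fit the later 'or less' entries. If those acted before patient five, the savings would be smaller:

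- Grade ≥3 at 40%: 0.243 − 0.4⁴ × 1 = 0.22.
- Grade 4 at 30%: 0.654 − (0.3³ × 2 + 3 × 0.3² × 0.7 × 0.3 × 1) = 0.654 − 0.111 = 0.54.

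**5. Effect of deleting the five-patient clause.** The criterion would then also be met by 2/2 Grade ≥3 events: lower limit 0.316, above 0.20. From 2/2, reaching 3/5 is not certain; at a true 20% rate its chance is 1 − 0.8³ = 48.8%. Adding 2/2 as a trigger to the listed limits raises the per-arm suspension probability at 20% from 14.8% to 16.3%.

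**The case against.** The strongest objections concern size and remedy.

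- **The five-patient clause has a use.** A reader might infer that it can be struck out at no cost. Step 5 shows otherwise: it holds back 2/2 Grade ≥3, which is not decisive. This objection stands.
- **The clause does not say the five are per arm.** That reading comes from the list. If the five are trial-wide, an arm may hold fewer than five when the criterion starts to apply, so 3/3 or 2/2 could meet it while the list still has no entry. The two statements then disagree, so this changes the form of the gap but does not close it.
- **Events are not seen at accrual.** A reader might infer 2.4 or 3.6 months of avoidable accrual (2 or 3 patients at 18/15 = 1.2 months each). In Arm 2 the DNA vaccine starts on day 43, about 1.4 months. With even accrual, patient 3 enters at 2.4 months and cannot have a vaccine event before about 3.8, when patient 4 (3.6 months) is already in. The maximum fits only early events, such as reactions to sipuleucel-T.
- **Other safeguards exist.** A reader might infer that nothing can halt accrual before patient five. Section 14 has serious events reported to the DSMC Chair, who decides whether immediate action is needed, and provides for suspension or closure for significant risk. Section 16.B adds weekly review, and Section 8 stops vaccination in a patient with a Grade 4 event. These are discretionary or patient-level, so they reduce the consequence but do not supply the missing numerical trigger.

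**Conclusion.** The gap in the listed limits is real, and its effect is small. The plan's own criterion is met at 3/3 and 3/4 (Grade ≥3) and at 2/2 to 2/4 (Grade 4), suspension at patient five is then certain, and the list does not call for it sooner. Closing the gap costs nothing in false suspensions, provided the change is confined to those counts.

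This rests on exact binomial limits, which reproduce the plan's list, on per-arm counting, and on events being known before the next patient enters. The last assumption favours the change, so the average savings are upper figures, particularly for vaccine events. The documents do not support the stronger conclusions that early suspension is forbidden or that the five-patient clause serves no purpose.

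**What to change.** 1. In Section 6.A, write the first entries as *3 out of 5 (or less)* for Grade ≥3 and *2 out of 5 (or less)* for Grade 4, leaving the other limits unchanged.
2. State that the operational list governs accrual suspension. This also settles counts such as 3/6 and 2/2 Grade ≥3, which meet the criterion but are not listed.
3. Reconcile the five-patient clause with the list and say whether the five are per arm or trial-wide. One way is to limit the clause to counts that do not already guarantee crossing at patient five.

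The cost is a wording amendment. No extra data are needed, and the chance of ever suspending under the listed limits does not change.
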